50.01 B7-H4 positive ovarian cancer

50.02 Histologically or cytologically confirmed diagnosis of recurrent epithelial ovarian, primary peritoneal, or fallopian tube carcinoma that is refractory to existing therapy(ies) known to provide clinical benefit

50.03) Progressive disease on or after at least two prior regimens of treatment including at least one platinum-containing regimen, *or* unable to tolerate additional chemotherapy

50.04) No prior therapy with an anti-PD1 or PD-L1-directed agent

5.1.2 Phase 1b Inclusion Criteria (Monotherapy and Combination Therapy)

Patients enrolling into **Phase 1b** must meet *all* of the following inclusion criteria:

- 18) All Inclusion Criteria for Phase 1a (Exception: Phase 1a Inclusion Criterion #1).
- 19) Positive for B7-H4 expression in an archival or fresh tumor sample as evaluated by an accompanying validated central laboratory IHC assay. Archival tissue for patients enrolled in Cohort 1b1 (Breast Cancer) must be within 24 months prior to pre-screening.
- 20) History of other malignancy is permitted provided it has been definitively treated with no evidence of recurrence within the past 2 years (Exception: Definitively treated non-melanoma skin cancer, lobular cancer in situ, and cervical cancer in situ within 2 years are permitted).

5.1.3 Additional Cohort-Specific Inclusion Criteria for Phase 1b (Monotherapy and Combination Therapy)

Cohort 1b1 Breast Cancer

Triple Negative Breast Cancer (TNBC)

21.01) Histologically or cytologically confirmed metastatic TNBC

21.02) At least two prior lines of systemic chemotherapy with at least one being administered in the metastatic setting

HR+ Breast Cancer

21.03) Histologically or cytologically confirmed metastatic HR+ breast carcinoma

21.04) Patients must have received at least two prior lines of hormonal therapy

21.05) Patients must have received at least one prior line of systemic chemotherapy (in the adjuvant or metastatic setting)

Cohort 1b2 Ovarian Cancer

22.01) Histologically or cytologically confirmed diagnosis of recurrent epithelial ovarian, primary peritoneal, or fallopian tube carcinoma that is refractory to existing therapy(ies) known to provide clinical benefit

22.02) Progressive disease on or after at least two prior regimens of treatment including at least one platinum-containing regimen, or unable to tolerate additional chemotherapy

Cohort 1b3 Endometrial Cancer

23.01) Histologically or cytologically confirmed recurrent or persistent endometrial cancer that is refractory to curative or established treatments

23.02) Progressive disease on or after at least one prior regimen of systemic chemotherapy, or unable to tolerate systemic chemotherapy

Cohort 1bC1 Ovarian Cancer

24.01) Histologically or cytologically confirmed diagnosis of recurrent epithelial ovarian, primary peritoneal, or fallopian tube carcinoma that is refractory to existing therapy(ies) known to provide clinical benefit

24.02) Progressive disease on or after at least two prior regimens of treatment including at least one platinum-containing regimen, *or* unable to tolerate additional chemotherapy

24.03) No prior therapy with an anti-PD1 or PD-L1-directed agent

No waivers will be granted for any of these inclusion criteria.

5.2 Eligibility Criteria

Exclusion Criteria (Phase 1a And Phase 1b)

Patients who meet ANY of the following criteria will be excluded from study entry:

- 1) Immunosuppressive doses of systemic medications, such as steroids or absorbed topical steroids (doses > 10 mg/day prednisone or equivalent daily) must be discontinued at least two weeks before the first dose of study drug. Short courses of high dose steroids, continuous low dose (prednisone < 10 mg/day), inhaled, intranasal, intraocular, and joint injections of steroids are allowed
- 2) Decreased cardiac function with New York Heart Association (NYHA) > Class 2 at screening
- 3) Uncontrolled or significant heart disorder such as unstable angina
- 4) QT interval corrected for heart rate (QTc) per institutional guidelines > 450 msec for males or > 470 msec for females at screening
- 5) History of ADAs, , severe allergic, anaphylactic, or other infusion-related reaction to a previous biologic agent
- 6) Known hypersensitivity to any component of the investigational product (IP) formulation including active ingredient, sodium acetate, sucrose, and polysorbate 20 (refer to Section [6.1.1](#))

- 7) Vaccines (eg, human papilloma virus [HPV] vaccine) within 4 weeks before the first dose of study drug. The inactivated seasonal influenza vaccine can be given to patients before treatment and while on therapy without restriction. Influenza vaccines containing live virus or other clinically indicated vaccinations for infectious diseases (ie, pneumovax, varicella, etc.) may be permitted, but must be discussed with the Sponsor's Medical Monitor and may require a study drug washout period prior to and after administration of the vaccine.
- 8) Current unresolved infection or history of chronic, active, clinically significant infection (viral, bacterial, fungal, or other) which, in the opinion of the Investigator, would preclude the patient from exposure to a biologic agent or may pose a risk to patient safety.
- 9) Patients with abnormal serum chemistry values that in the opinion of the Investigator are considered to be clinically significant. This includes patients who show clinical signs and symptoms related to their abnormal serum chemistry values, as well as patients whose serum chemistry values are asymptomatic, but clinically significant according to the Investigator (eg, hypokalemia or hyponatremia).
- 10) Any uncontrolled medical condition or psychiatric disorder which, in the opinion of the Investigator, would pose a risk to patient safety or interfere with study participation or interpretation of individual patient results
- 11) Pregnant or breastfeeding
- 12) Active, known, or suspected autoimmune disease. Patients with Type I diabetes mellitus, hypothyroidism requiring only hormone replacement, skin disorders (such as vitiligo, psoriasis, or alopecia) not requiring systemic treatment, or conditions not expected to recur in the absence of an external trigger, are permitted to enroll.
- 13) Known history of testing positive for human immunodeficiency virus (HIV) 1 or 2 or known acquired immunodeficiency syndrome (AIDS).
- 14) Positive test for hepatitis B virus surface antigen (HBsAg) or detectable hepatitis C virus ribonucleic acid (HCV RNA) indicating acute or chronic infection.
- 15) Ongoing adverse effects from prior treatment > Grade 1 (with the exception of Grade 2 alopecia or peripheral neuropathy) based on National Cancer Institute (NCI) Common Terminology Criteria for Adverse Events (CTCAE).
- 16) Symptomatic interstitial lung disease or inflammatory pneumonitis.
- 17) Untreated or active CNS or leptomeningeal metastases. Patients are eligible if metastases have been treated and patients are neurologically returned to baseline or neurologically stable (except for residual signs or symptoms related to the CNS treatment) for at least 2 weeks before the first dose of study drug.
- 18) Evidence of coagulopathy or bleeding diathesis. Patients receiving stable therapeutic doses of anti-coagulants will be permitted.

- 19) Transfusion of blood or platelets completed within 72 hours before the first dose of study drug.
 - 20) Any uncontrolled inflammatory GI disease including Crohn's Disease and ulcerative colitis
 - 21) For Cohort 1b1 only: Patients with HER2 positive disease
- No waivers will be granted for any of these exclusion criteria.

5.3 Lifestyle Restrictions

There is not enough information currently available to make any specific recommendations regarding lifestyle restrictions.

5.4 Screen Failures

Patients in the Phase 1a Dose Exploration and in Phase 1b Dose Expansion who test negative for B7-H4 will be considered Pre-Screen-Failures. Patients who test positive and enter the Screening Period, but do not enroll, will be considered Screen-Failed.

6 Treatments

6.1 Treatments Administered

6.1.1 FPA150 Identity

FPA150 drug product is supplied for IV administration as a sterile, aqueous, colorless to slightly yellowish, pyrogen-free solution supplied in single-use glass vials. The composition of the drug product contains 20 mg/mL active ingredient, 20 mM sodium acetate, 270 mM sucrose, 0.05% (w/v) polysorbate 20 at pH 5.0. The container-closure system consists of a 5 mL Type I glass vial, sealed with a bromobutyl rubber stopper, and a flip-off cap. The final drug product will be provided as 2° to 8°C refrigerated liquid protected from light which is diluted for administration according to instructions provided in a separate Pharmacy Manual.

A 20 mL vial will be available in the second half of 2019. The composition of the drug product contains 20 mg/mL active ingredient, 20 mM sodium acetate, 270 mM sucrose, 0.05% (w/v) polysorbate 20 at pH 5.0. The container-closure system consists of a 20 mL Type I glass vial, sealed with a bromobutyl rubber stopper, and a flip-off cap.

FPA150 will be supplied in a sterile vial for dilution into an IV bag for administration by the study center.

6.1.2 Pembrolizumab

Pembrolizumab for injection is a sterile, preservative-free, clear to slightly opalescent, colorless to slightly yellow solution that requires dilution for intravenous infusion. Each vial contains 100 mg of pembrolizumab in 4 mL solution. Each 1 mL solution contains 25 mg of pembrolizumab and is formulated in: L-histidine (1.55 mg), polysorbate 80 (0.2 mg), sucrose (70 mg) and Water for Injection. For additional information, refer to the Keytruda® (pembrolizumab) Prescribing Information (Keytruda® USPI). FPA150 + pembrolizumab combination cohorts will only enroll in the United States.

Pembrolizumab is available for injection as a 50 mg lyophilized powder in single-use vial for reconstitution and in 100 mg/4 mL (25 mg/mL) solution in single use vial.

The lyophilized powder is reconstituted by adding 2.3 mL of Sterile Water for Injection, USP by injecting the water along the walls of the vial and not directly on the lyophilized powder (resulting concentration 25 mg/mL). Slowly swirl the vial and allow up to 5 minutes for the bubbles to clear. Do not shake the vial.

The injection is a sterile, preservative-free, clear to slightly opalescent, colorless to slightly yellow solution that requires dilution for intravenous infusion. . Each 1 mL of solution contains 25 mg of pembrolizumab and is formulated in: L-histidine (1.55 mg), polysorbate 80 (0.2 mg), sucrose (70 mg) and water for Injection. Please refer to pembrolizumab USPI

6.2 Treatment Packaging, Labeling, and Storage

6.2.1 FPA150

FPA150 will be packaged and labeled as a 5 mL or 20 mL (to be available in second half of 2019) fill in ISO 6R vials by the Sponsor (or designee) per applicable local regulatory requirements.

All FPA150 vials must be stored refrigerated at 2° to 8°C in accordance with the manufacturer's instructions as provided in the Pharmacy Manual. Until dispensed to patients, FPA150 will be stored in a securely locked area, accessible to authorized personnel only.

6.2.2 Pembrolizumab

For the combination cohorts pembrolizumab's .

packaging, labelling, and storage of pembrolizumab should be in accordance with the Keytruda® USPI , the Pharmacy Manual, and relevant local guidelines.

6.3 Administration and Preparation

6.3.1 FPA150

FPA150 will be administered as a 60-minute IV infusion Q3W in 21-day cycles until progressive disease or unacceptable toxicity. Proposed dose levels to be studied are outlined in [Table 3](#) for Phase 1a Dose Escalation. Please refer to the pharmacy manual for any additional dosing instructions for dose levels below 1 mg/kg.

The dose of FPA150 will be based on body weight at Cycle 1 Day 1. After Cycle 1, the FPA150 dose will be recalculated at each infusion visit only if the patient's weight has changed > 10% from Cycle 1, Day 1.

Further instructions on drug preparation and administration are in the Pharmacy Manual.

There is no pre-specified maximum number of doses of FPA150 monotherapy. Patients may continue receiving FPA150 according to their study specified cohort/ dose until Investigator-assessed clinical progression, unacceptable toxicity, or until the patient meets any of the other protocol-specified withdrawal criteria.

A pharmacist (or other responsible person) will prepare FPA150 for administration. After calculating the number of vials based on the patient's weight, FPA150 will be diluted in a 0.9% sodium chloride solution or 5% dextrose in water solution. Prepared FPA150 should be administered ≤4 hours after preparation under ambient temperature.

FPA150 will be administered under medical supervision over approximately 60-minute (± 5 minutes) IV infusion via a peripheral vein or central venous catheter. The IV administration set for FPA150 infusion must contain a 0.22 μm in-line filter or a 0.22 μm syringe filter.

All patients must be monitored for at least 4 hours after the end of the first infusion of FPA150. Patients in whom inpatient dose escalation is planned (ie, patients enrolled at dose levels below 1 mg/kg) should also be monitored for at least 4 hours after the end of infusion at each dose escalation. Infusion of FPA150 must be stopped, reduced, interrupted, or discontinued according to Section 6.4.4 (Dose Modification Criteria) and Section 6.4.6 (Dose Interruptions During Study Treatment Administration). If a patient experiences an infusion reaction, the patient's vital signs (temperature, blood pressure, pulse, and respiration rate) should be monitored during the infusion as well as every 30 minutes after the infusion for a minimum of 2 hours and until resolution of the infusion reaction.

6.3.2 Pembrolizumab

Pembrolizumab should be prepared according to the Keytruda® USPI.

Table 9 details the treatment regimen for the combination cohorts. Pembrolizumab will be administered after completion of the FPA150 IV infusion. Pembrolizumab will be administered at a dose of 200 mg by IV infusion over 30 minutes (± 5 minutes) starting on C1D1 and repeated Q3W on Day 1 of each 21-day cycle after all procedures and assessments have been completed. Pembrolizumab should not be co-administered with FPA150.

Further information regarding dosing and preparation of pembrolizumab can be found in the Keytruda® USPI.

Table 9: Study Treatment Regimen of Combined Treatment of FPA150 and Pembrolizumab

Study Treatment	Dosage Formulation	Unit Dose Strengths	Dosage Level (s)	Route of Administration	Regimen/ Treatment Period
FPA150	Solution for infusion	Single-use glass vials (5 mL and 20 mL) containing 20 mg/mL active ingredient	Table 4	60-minute (± 5 minutes) IV infusion	Day 1 of each cycle (Q3W) 30 to 60 minutes
Pembrolizumab	Solution for infusion or lyophilized powder	100 mg/vial containing 25 mg/mL active ingredient or 50 mg lyophilized powder in single use vial for reconstitution	200 mg	30-minute IV infusion	Day 1 of each 21-day cycle (Q3W) After FPA150

6.4 Dose Modifications

In Phase 1a the starting dose level of FPA150 is 0.01 mg/kg. Subsequent dose escalations between cohorts in Phase 1a are described in Section 4.1.1. The dose of FPA150 for Phase 1b will be determined by evaluation of the data from Phase 1a of the study, as described in Section 4.1.4.

All patients in the combination cohorts receive pembrolizumab 200 mg IV Q3W. Dose modifications for pembrolizumab are described in the package insert. Dose reductions for pembrolizumab are not permitted.

6.4.1 Dose Modification Based on Weight

A complete physical examination including height and weight will be performed at screening. The dose of FPA150 will be based on body weight at Cycle 1 Day 1. After Cycle 1, the FPA150 dose will be recalculated at each infusion visit only if the patient's weight has changed > 10% from Cycle 1, Day 1.

The dose of pembrolizumab will not be adjusted based on weight.

6.4.2 Dose Escalation within a Cohort

In Phase 1a, inpatient dose escalation will be permitted in patients enrolled at dose levels below 1 mg/kg provided:

- The patient did not experience a DLT
- All other AEs have recovered to Grade 1 or lower prior to dose escalation
- The patient may only dose escalate by a maximum of 1 dose level every 21 days
- The patient cannot dose escalate beyond 1mg/kg dose level unless the dose level has been cleared according to the standard 3+3 dose escalation design as described in Section 4.1
- Patients treated at dose levels up to 1 mg/kg may be escalated to a higher dose level if the patient has had a radiographic response, subsequently progressed and the higher dose levels have cleared DLT.

Inpatient dose escalation will only be permitted after a discussion between the sponsor medical monitor and treating physician taking into account the overall safety experience, PK and PD data available at the time of the request.

In Phase 1b, patients will be treated at the MTD and/or RD as determined from Phase 1a, and dose escalation will not be permitted.

6.4.3 Toxicity at Lowest Dose Level

If the MTD is unexpectedly exceeded at the first dose level of FPA150 (0.01 mg/kg), the dose may be reduced to 0.005 mg/kg (refer to [Table 3](#) for an outline of FPA150 dose levels for Phase 1a). Decisions on how to next proceed will be based on safety, tolerability, and PK data, and will be determined by the CRC (refer to [Section 4.1.1](#)).

6.4.4 Dose Modification Criteria for FPA150

Dose reductions for FPA150 may be permitted for patients on treatment beyond the DLT Period and can be assessed using local laboratories. If a patient requires a dose reduction of FPA150 during the DLT period, they will be considered to have a DLT and be permanently discontinued from FPA150. Dose reductions for FPA150-related AEs should follow the guidelines outlined in [Table 10](#). The treating physician may choose to interrupt or discontinue FPA150 at any time outside of these guidelines if they believe it is necessary to ensure patient safety. It is recommended that the treating physician discuss the proposed dosing modification with the FivePrime medical monitor prior to making the change. Patients may resume FPA150 if the event returns to baseline or \leq Grade 1 in accordance with the guidelines outlined in [Table 10](#). Any variations from these guidelines must be discussed with the FivePrime Medical Monitor prior to dosing and must take into consideration the overall benefit and risks for the patient of continued participation in the study.

Table 10: Dose Modification Guidelines for FPA150 (Non-infusion Toxicity)

FPA150-related Toxicity Grade	Dose Schedule	New FPA150 Dose
Grade 1 or 2	No delay or missed dose required	100% of dose
Grade 3 (first occurrence)	Delay or miss dose until recovery to baseline or Grade 1	If recovery to baseline or Grade 1 within 28 days, may resume at 100% of starting dose or 1 dose lower ^a
Grade 3 (second occurrence)	Delay or miss dose until recovery to baseline or Grade 1	If recovery to baseline or Grade 1 within 28 days, may resume at 1 level lower ^a than previous dose or discontinue
Grade 3 (third occurrence) Grade 3 which does not recover to baseline or Grade 1 within 28 days Any Grade 4	Permanently Discontinue	N/A

^a Eg, 1 dose level lower for patients treated at 20 mg/kg is 10 mg/kg; 1 dose level lower for patients treated at 10 mg/kg is 3 mg/kg; 1 dose level lower for patients treated at 3 mg/kg is 1 mg/kg.

There is a \pm 3-day window for the first 3 scheduled FPA150 dosing visits. The first dose of each cycle is considered Day 1 of each cycle. Cycles will repeat every 21 days unless there is a treatment delay. Inpatient dose escalation will not be permitted above 1mg/kg except as detailed in [Section 6.4.2](#). Any patient whose dose of FPA150 is decreased cannot be subsequently increased.

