The DLT evaluation interval begins on the first day of treatment upon start of infusion and continues for 21 days. In Phase 1a Monotherapy Dose Escalation, patients' second dose must be at least 21 days after the first dose. Patients who receive at least one dose of study drug during the 21-day evaluation interval, or patients who discontinue study treatment for drug-related AEs before the DLT evaluation interval is complete, will be considered evaluable for DLT determination. In consultation with Investigators, the Sponsor may open cohorts at dose levels between the dose levels proposed in the protocol.

An accelerated titration design enrolling at least 1 patient at each dose level is planned for dose levels 0.01, 0.03, 0.1 and 0.3 mg/kg. Dose escalation to the next dose level may proceed after at least 1 patient completes the 21-day evaluation interval. If a single patient experiences a DLT or at least 2 patients experience moderate AEs (at any dose level) during the 21-day evaluation interval, additional patients will be enrolled at the current dose level and standard 3+3 dose escalation criteria will apply for that cohort as well as all subsequent dosing cohorts.

Moderate AEs are defined as \geq Grade 2 AEs regardless of attribution (except for those events clearly due to the underlying disease or extraneous causes). Grade 2 laboratory values will not be considered as moderate AEs for this purpose unless accompanied by clinical sequelae.

The algorithm outlined in the table below will be used for all standard 3+3 dose escalation decisions in Phase 1a Monotherapy Dose Escalation. If not already applied at a lower dose level according to the criteria stated above, enrollment at all dose levels \geq 1 mg/kg will follow a standard 3+3 dose escalation design.

Algorithm for 3+3 Dose Escalation Decisions in Phase 1a Monotherapy Dose Escalation:

Number of Patients with DLT at a Given Dose Level	Dose Escalation Decision Rule
0/3	Enroll 3 patients at next dose level (next/higher cohort)
1/3	Enroll 3 additional patients at current dose level (current cohort)
$\geq 2/3$	Stop enrollment. Enter 3 more patients at the previous dose level (previous/lower cohort), if only 3 were previously entered, or at an intermediate dose level
1/6	Enroll 3 patients at next dose level (next/higher cohort)
$\geq 2/6$	Stop enrollment. Enter 3 more patients at the lower dose level (previous/lower cohort), if only 3 were previously entered, or at an intermediate dose level

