The DLT evaluation interval begins on the first day of treatment upon start of infusion and continues for 21 days. The algorithm outlined in the table below will apply for dosing decisions. The dose of FPA150 may be lowered as needed in response to DLTs. The MTD and/or RD of FPA150 in combination with pembrolizumab will be a dose where $\leq 1/3$ -6 patients encounter a DLT.

Algorithm for Dose De-Escalation Decisions for Phase 1a Combination Safety Lead-In

Number of Patients with DLT at a Given Dose Level	Dosing Decision Rule
0/3	Proceed with enrollment of up to 10 total patients at that dose level for additional safety assessment
1/3	Enroll 3 additional patients at current dose level (current cohort)
$\geq 2/3$	Stop enrollment at current cohort and de-escalate FPA150 to one dose level below current dose
1/6	Proceed with enrollment of up to 10 total patients at that dose level
$\geq 2/6$	Stop enrollment at current cohort and de-escalate FPA150 to one dose level below current dose.

Phase 1b FPA150 Monotherapy and Phase 1b Combination Dose Expansion:

Enrollment in Phase 1b will begin when the MTD and/or RD has been identified by the CRC. The MTD and/or RD determination will be based on overall safety, tolerability, objective response, PK, and pharmacodynamics from the Phase 1a Monotherapy Dose Escalation and Phase 1a Combination Safety Lead-In portions of the study and estimates of efficacious exposures extrapolated from nonclinical data.

Phase 1b will initially consist of cohorts of up to 30 patients each in the following 3 tumor types with B7-H4 expression levels determined by IHC. There will be three FPA150 monotherapy cohorts and one FPA150 combination cohort at the MTD and/or RD:

Phase 1b Expansion Cohorts, Tumor Types, and Therapy

Cohort	Tumor Type	Therapy Type (Monotherapy or Combination)
1b1	Breast cancer	Monotherapy: FPA150
1b2	Ovarian cancer	Monotherapy: FPA150
1b3	Endometrial cancer	Monotherapy: FPA150
1bC1	Ovarian cancer	Combination: FPA150 with pembrolizumab

Based on emerging clinical and translational data from the study, cohorts for additional tumor types with FPA150 as monotherapy or in combination may be opened during the trial (not to exceed 30 patients in any individual cohort and not exceed 7 cohorts).

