4.1.2.2.2 FPA150 Combined with Pembrolizumab (Safety Lead-in)

Additional DLT Considerations for the Combination of FPA150 and Pembrolizumab

Because pembrolizumab is a known immune checkpoint inhibitor and one of the proposed mechanisms of action of FPA150 is immune checkpoint blockade, immune-related adverse events (irAEs) are anticipated with this combination. An irAE is defined as a clinically significant AE that is associated with study drug exposure, of unknown etiology, and is consistent with an immune-mediated mechanism. Based on that background, the first occurrence of the following irAEs will not be considered a DLT because they are expected with immune therapy:

- Grade 3 tumor flare (defined as local pain, irritation, or rash localized at sites of known or suspected tumor)
- Grade 3 rash
- Grade 3 immune-related adverse event (irAE) that resolved to a Grade 1 or less within 14 days
- Transient (resolving within 6 hours of onset) Grade 3 infusion-related AE

A second occurrence of these events (except Grade 3 tumor flare) either in the same or different patient during the DLT period will be considered a DLT

4.1.2.3 Dose-Limiting Toxicity Evaluation and Dose Escalation (FPA150 Monotherapy and Combination Safety Lead-in)

The DLT evaluation interval begins on the first day of treatment upon start of infusion and continues for 21 days. In Phase 1a Dose Escalation, patients' second dose must be at least 21 days after the first dose.

Review of safety, PK and pharmacodynamic profiles may inform decisions to add cohorts with alternative dose levels or dose regimens (eg, different dosing frequency, higher dose levels) in order to reach an optimal target exposure.

All dose escalation decisions will be based on the assessment of DLTs and overall safety and tolerability, and will be made after the last patient enrolled in each cohort has completed the first treatment cycle (ie, 21 days). Dose escalation decisions will be agreed upon by the CRC as outlined in Section [4.1.1](#).

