APPENDIX 4:	EASTERN COOPERATIVE ONCOLOGY GROUP PERFORMANCE STATUS.....	120
APPENDIX 5:	CLINICAL LABORATORY TESTS.....	121
APPENDIX 6:	NEW YORK HEART ASSOCIATION CLASSIFICATION.....	123
APPENDIX 7:	PROTOCOL AMENDMENT HISTORY	124

APPENDIX 1: SCHEDULE OF ASSESSMENTS**Table 12: Schedule of Assessments: Phase 1a and Phase 1b (Monotherapy and Combination Cohorts)**

Procedure ^{a,b}	Pre-Screening	Screening	Cycle 1		Cycle 2	Subsequent Cycles	End of Treatment Follow-up Period		LTFU Period ^p
		Day -28 to Day 0	Day 1 ^q ± 3 days	Day 8 ± 3 days	Day 1 ± 3 days	Day 1 ± 3 days	28 (±7) days post-last dose	100 (±7) days post-last dose	
Informed Consent	x ⁱ	x							
Review / Confirm Eligibility Criteria		x	x						
Medical History / Demographics		x	x						
Physical Examination ^c		x	x	x	x	x	x	x	
Height and Weight ^{c,d}		x	x		x	x	x	x	
Vital Signs ^e		x	x	x	x	x	x	x	
12-Lead ECG ^f		x					x	x	
ECOG Performance Status ^g		x	x		x	x	x	x	
Fresh Biopsy ^h		x				x			
Archival Tissue for IHC Testing for B7-H4 and Exploratory Biomarker Analyses ⁱ	x	x							
Clinical Safety Laboratory Tests ^j		x	x	x	x	x	x	x	
Hepatitis B (HBsAg and HBcAb), and Hepatitis C (HCV RNA)		x							
CT/MRI Tumor Assessment ^k		x				x	x		x
Tumor Markers ^l	Refer to Appendix 2 for specific days and times								
Pregnancy Test ^m		x	x			x	x		
Sampling for PK, ADA, and Pharmacodynamics ⁿ	Refer to Appendix 2 for specific days and times								

Procedure ^{a,b}	Pre-Screening	Screening	Cycle 1		Cycle 2	Subsequent Cycles	End of Treatment Follow-up Period		LTFU Period ^p
		Day -28 to Day 0	Day 1 ^q ± 3 days	Day 8 ± 3 days	Day 1 ± 3 days	Day 1 ± 3 days	28 (±7) days post-last dose	100 (±7) days post-last dose	
Study Drug(s) ^o			x		x	x			
Adverse Events ^s			x	x	x	x	x		
Prior/Concomitant Medications			x	x	x	x	x		
Thyroid Function Testing ^f			x			x			
Long-Term Follow-up Contact ^p									x

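### The ±3-day dosing window lets dose 2 fall inside the 21-day DLT window, against the 21-day minimum interval, and it is unclear whether that minimum covers the Combination Safety Lead-in

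*Protocol*

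**What the plan says.** **The window.** Protocol Section 6.4.4 gives a plus-or-minus "3-day window for the first 3 scheduled FPA150 dosing visits". It adds "The first dose of each cycle is considered Day 1 of each cycle" and "Cycles will repeat every 21 days unless there is a treatment delay". It makes no exception for dose 2 or for patients under DLT evaluation. Appendix 1 Table 12 is headed "Schedule of Assessments: Phase 1a and Phase 1b (Monotherapy and Combination Cohorts"), so one schedule serves every part of the study. Its Cycle 2 column shows Day 1 with ±3 days, and study drug is marked there. Footnote a to that table makes ±72 hours a default that gives way where something else is specified.

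**The minimum interval.** Section 4.1.2.3 says: "In Phase 1a Dose Escalation, patients' second dose must be at least 21 days after the first dose". The synopsis states the same rule but opens it with "In Phase 1a Monotherapy Dose Escalation, patients", which names monotherapy only.

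**The DLT window.** For the Combination Safety Lead-in, the synopsis says: "The DLT evaluation interval begins on the first day of treatment upon start of infusion and continues for 21 days". That lead-in text gives no minimum interval between doses. In the protocol body, the heading of Section 4.1.2.3 names both monotherapy and the lead-in. The lead-in itself is Section 4.1.2.1, within the section on Phase 1a Dose Escalation.

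**Pembrolizumab.** Section 6.3.2 places it after the FPA150 infusion on Day 1 of each cycle, so it moves with the FPA150 visit.

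**The concern.** A site that follows Section 6.4.4 or the Cycle 2 column of Table 12 may give dose 2 before the DLT window has closed. A site that follows Section 4.1.2.3 may not, at least in monotherapy escalation. For the lead-in, the documents do not settle which rule holds.

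The dose-2 date affects how events are classified:

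- Under Section 6.4.4, a patient who needs an FPA150 dose reduction during the DLT period is counted as having a DLT and stops FPA150. After that period a reduction may be allowed. A reduction decided at the dose-2 visit could fall under either rule, depending on the visit date.
- Under Section 4.1.2.2.2, certain immune-related and infusion-related events are exempt the first time. Apart from Grade 3 tumor flare, a second occurrence in the same or another patient during the DLT period is a DLT. A second infusion inside the window adds an opportunity for one.
- Under Section 6.4.5, any pembrolizumab modification for related toxicity in the lead-in is a DLT. An early dose 2 is another occasion for such a decision inside the window.

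Table 6 decides on 3 or 6 patients, so a single event can change the action taken.

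**Working it through.** The plan gives no figure to reproduce, so the check is date arithmetic.

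**Inputs**
- Dose 1 = study day 1 (Section 6.4.4: a cycle's first dose is its Day 1).
- Cycle length = 21 days (Section 6.4.4).
- Visit window = −3 to +3 days (Section 6.4.4; Table 12, Cycle 2).
- Minimum interval = 21 days (Section 4.1.2.3; synopsis).
- DLT window = 21 days from the start of the first infusion, counted here as study days 1 to 21.

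**Formulas**
- Study day of dose 2 = 1 + 21 + offset.
- Interval = study day of dose 2 − 1.
- DLT days from dose 2 onward, dose day included = max(0, 21 − study day of dose 2 + 1).

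| Offset (days) | Study day of dose 2 | Interval (days) | Meets 21-day minimum | Inside DLT window | DLT days from dose 2 onward |
|---|---|---|---|---|---|
| −3 | 19 | 18 | no | yes | 3 |
| −2 | 20 | 19 | no | yes | 2 |
| −1 | 21 | 20 | no | yes | 1 |
| 0 | 22 | 21 | yes | no | 0 |
| +1 | 23 | 22 | yes | no | 0 |
| +2 | 24 | 23 | yes | no | 0 |
| +3 | 25 | 24 | yes | no | 0 |

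The three early offsets all break the minimum and all put dose 2 inside the DLT window. In the worst case 3/21 = 14% of the DLT days follow a second dose, and the days before dose 2 fall from 21 to 18. Counting elapsed 24-hour days from the infusion would not take days 19 to 21 out of the window.

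**The lead-in under each reading**
- *Body reading.* The heading of Section 4.1.2.3 and the place of the lead-in within Section 4.1.2 bring the lead-in under the minimum. Section 6.4.4 and the Cycle 2 column of Table 12 are then inconsistent with it.
- *Synopsis reading.* The minimum belongs to monotherapy escalation only. The lead-in then has a 21-day DLT window, a ±3-day visit window and no stated minimum, so dose 2 of both drugs is permitted on study days 19 to 21.

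**Reach into the decision rule (Table 6).** One additional counted event turns 0/3 (proceed, up to 10 patients in total) into 1/3 (enroll 3 more), or 1/6 (proceed, up to 10 in total) into 2/6 (stop and de-escalate). That holds for a DLT on any day. It shows how sensitive the rule is, not how large the window's effect is.

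**The case against.** **The rules can be read together.** Footnote a makes the Table 12 window a default, and a stated minimum is a specification that displaces it. The offsets from 0 to +3 days satisfy every rule at once, so a permissive window and a mandatory floor may simply define a narrower range. This largely answers the point as far as Table 12 is concerned. It does not answer Section 6.4.4, which states its window without qualification or cross-reference. Nor does it help the lead-in on the synopsis reading, where no minimum is specified to displace the default.

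**The minimum may already cover the lead-in.** Section 4.1.2.3 names the lead-in in its heading, and its accelerated-titration paragraph is expressly limited to monotherapy, which suggests that other rules there apply to both parts. This is a fair reading. A reader might infer that lead-in patients will be re-dosed inside the DLT window. The documents support only that the synopsis leaves this open.

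**Dosing before committee review.** A reader might infer that an early dose 2 pre-empts the Cohort Review Committee. Nothing makes a patient's own dose 2 wait for that review. Decisions follow the last patient's first cycle, so patients enrolled sooner can receive dose 2 before the review even on study day 22.

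**A single-dose window.** A reader might infer that the DLT window is meant to observe exactly one dose. No passage says so, and the DLT-evaluable sets in Protocol Section 9.2 and SAP Section 3.1.3 require two doses, or a DLT in Cycle 1.

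**Direction and size.** Extra exposure on days 19 to 21 can add counted DLTs but not conceal any. Section 4.1.2.4 has the recommended dose take account of toxicity beyond the DLT period, and Table 10 already delays dosing after a related Grade 3 event. The 14% is a worst-case share of days, not an effect size. All of this stands and limits the weight of the point.

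**Conclusion.** The inconsistency is real. Section 6.4.4 permits dose 2 at 18 to 20 days with no exception, while Section 4.1.2.3 and the synopsis require at least 21 days in escalation. The scope of that minimum also differs between the synopsis and the protocol body. Whether lead-in patients may receive dose 2 of both drugs inside the DLT window therefore depends on which text a site follows.

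The size is modest: at most 3 of 21 DLT days, in a part of the study planned for 6 to 22 patients. The possible bias runs toward more counted DLTs, not fewer. The conclusion assumes study days 1 to 21 as the DLT window and pembrolizumab given at the FPA150 visit. The documents do not say how often visits run early, so no expected number of affected DLT counts can be given.

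A reader might extend the point to the completed monotherapy escalation. Section 4.1.2 records that its recommended dose was set as of 28 January 2019, before Amendment 2, and nothing in the documents shows that an early dose 2 occurred there. The practical relevance is mainly to the lead-in. The point should be corrected because it touches a rule that feeds DLT counts and costs almost nothing to settle.

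**What to change.** Reconcile Section 6.4.4, Table 12, Section 4.1.2.3 and the synopsis so that the permitted timing of Cycle 2 Day 1 for patients under DLT evaluation is stated once and consistently. State explicitly whether it applies to the Combination Safety Lead-in as well as to Monotherapy Dose Escalation. Which interval or window should hold is for the sponsor to decide, and none is proposed here.

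The cost is about one sentence in Section 6.4.4, one footnote in Table 12, and matching wording in Section 4.1.2.3 and the synopsis, made in an amendment. Depending on how the passages are reconciled, there may be slightly less scheduling flexibility at one visit for at most 22 lead-in patients.
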